11.0 SAFETY AND EVENT REPORTING

Subject safety and event reporting are important in this study. Investigators are responsible for ensuring that all safety events are recorded in the subject record(s). Events defined in Section 11.3 will be reported to the Sponsor, as applicable, per the timelines in Section 11.4.

11.1 Safety Oversight – Sponsor

Safety oversight will be under the direction of the Medical Director(s) of 3M, which is composed of individuals with the appropriate expertise. The Medical Director(s) routinely review and assess the safety data of the study.

11.2 Safety Recording and Reporting Requirements – Investigator

It is the responsibility of each participating Investigator to ensure all safety events are recorded in the subject’s record. The Investigator is responsible for reporting to the Sponsor safety events as defined in Section 11.44.

11.3 Safety and Event Reporting Definitions

This study utilizes the following definitions, as listed in the table below.

Table 11.3-1: Definitions

| Term | Definition |
|-----------------------------|--|
| Adverse Event (AE) | Any untoward medical occurrence, unintended disease or injury, or untoward clinical signs (including abnormal laboratory findings) in subjects, users or other persons, whether or not related to the investigational medical device. |
| Adverse Device Effect (ADE) | An adverse event related to the use of an investigational medical device. This includes any adverse events resulting from insufficient or inadequate instructions for use, deployment, implantation, installation, or operation, or any malfunction of the investigational medical device. This includes any event that is a result of a user error or intentional misuse of the investigational device. |
| Serious Adverse Event (SAE) | 
Any adverse event that:
 
 • Led to death • Led to serious deterioration in the health of the subject, that either resulted in 
 ○ a life-threatening illness or injury ○ a permanent impairment of a body structure or a body function ○ in-patient or prolonged hospitalization, ○ • medical or surgical intervention to prevent life-threatening illness or injury or permanent impairment to a body structure or a body function • Led to fetal distress, fetal death or a congenital anomaly or birth defect 
NOTE: Planned hospitalization for a pre-existing condition, or a procedure required by the Clinical Investigation Plan without serious deterioration in health, is not considered a SAE
 |

| Term | Definition |
|---|--|
| Serious Adverse Device Effect (SADE) | An adverse device effect that has resulted in any of the consequences characteristic of a serious adverse event |
| Unanticipated Serious Adverse Device Effect (USADE) | A serious adverse device effect, which by its nature, incidence, severity, or outcome has not been identified in the current version of the risk analysis report |
| Device Deficiency (DD) | An inadequacy of a medical device with respect to its identity, quality, durability, reliability, safety, or performance, such as malfunctions, use errors, and inadequate labelling |
| Complaint | Any written, electronic, or oral communication that alleges deficiencies related to the identity, quality, durability, reliability, safety, effectiveness, or performance of a device after it is released for distribution |

11.3.1 Severity Ratings

The table below defines the severity ratings for events. The Investigator shall ensure rating of reportable events on the applicable Case Report Form.

Table 11.3.1-1: Severity Ratings Definitions

| Term | Definition |
|-------------|---|
| Mild | An event that is easily tolerated by the subject, causing minimal discomfort and not interfering with everyday activities |
| Moderate | An event that is sufficiently discomforting to interfere with normal everyday activities |
| Severe | An event that prevents normal everyday activities |

11.3.2 Relatedness

The table below defines the relatedness definitions for events. The Investigator shall ensure rating of reportable events on the applicable Case Report Form.

Table 11.3.2-1: Relatedness Definitions

| Term | Definition |
|-------------|---|
| Not Related | Relationship to the device or procedure can be excluded |
| Possible | Relationship with the use of the study device is weak but cannot be ruled out completely. |
| Causal | The event is associated with the study device or with the procedures beyond a reasonable doubt when: 
 - The event is a known side effect of the device - The event has a temporal relationship with the study device/application procedures - The event involves a body/site or organ that 
 o The device or procedures are applied to; o The device or procedures have an effect on - The event follows a known response pattern to the device |

11.4 Safety and Event Sponsor Reporting Requirements

This study requires that the following events be reported to the Sponsor, in addition, to completing Case Report Form:

- Reportable Adverse Device Effects, as described in Section 3.3.2
- Any Adverse Events deemed by the Investigator to be related to participation in the study and considered to be due to the study intervention or comparator product.
- All Unanticipated Adverse Device Effects
- All Serious Adverse Events, Serious Adverse Device Effects, Unanticipated Serious Adverse Device Effects
- Device Deficiencies
Devices meeting the performance expectations but not exceeding performance expectations will NOT be captured as device deficiencies.
- Any Complaint related to any 3M commercially available product used in the study.

The Investigator shall report information relating to the event, and include dates of the event, severity rating, treatment, seriousness and relationship to the investigational device.

Any Adverse Events, which are not safety related, which are ongoing at the end of the study should be marked as “*persistent*” per study specific CRF. Any Events which related to safety OR are persistent and deemed related to the study device, may be followed for an additional 30 calendar days. Events reported by subjects after the last study visit may be reported to the Sponsor up to 30 calendar days from the date of the last visit.

11.4.1 Reporting Timelines

The table below indicates the reporting timelines for events to the Sponsor. The Investigator shall report to local IRB/EC and local regulatory authorities, per local requirements.

Reporting to Sponsor begins when study staff are aware of the event. For any event listed in the table below, study Sponsor may request additional information from the Investigator, including but not limited to, medical records, laboratory testing, radiological results, etc. regarding the event.

Table 11.4-1: Safety Reporting Timelines

| Type of event | Report to Sponsor | Method |
|--|--|--|
| Adverse Events (AE) deemed by the Investigator to be related to participation in the study and considered to be due to the study intervention or comparator product. | Per protocol visits/ Per month | Complete CRF |
| Unanticipated Adverse Device Effect (UADE) | Per protocol visits/ Per month | Complete CRF |
| Serious Adverse Event (SAE)/Serious Adverse Device Effect (SADE) | Within 24 hours of study staff becoming aware of event | Initial: Phone/Email to Sponsor Followed by: Complete CRF |
| Unanticipated Serious Adverse Device Effect (USADE) | Within 24 hours of study staff becoming aware of event | Initial: Phone/Email to Sponsor Followed by: Complete CRF |
| Device Deficiency (DD) | Within 3 business days of becoming aware of event | Complete CRF |

| | | |
|--------------------------------|---|--|
| 3M HealthCare | CLINICAL INVESTIGATION PLAN | CLIN-PROT-CIP-05-014894 Version: 2 Status: Release |
|--------------------------------|---|--|

| Type of event | Report to Sponsor | Method |
|---|---|--------------|
| Product Complaints on 3M Marketed Product | Within 3 business days of becoming aware of event | Complete CRF |

12.0 DEVIATIONS

A deviation is a departure from the Clinical Investigation Plan that will likely affect the safety, rights or welfare of subjects, the scope of the investigation or the scientific quality of the study. A deviation report form shall be completed per event per individual subject. Deviations are documented on a deviation report form or appropriate Case Report Form (CRF). The Investigator is responsible for reporting deviations to the reviewing IRB/EC, per local requirements.

12.1 Deviation Reporting Timelines

Table 12.1-1: Deviation Reporting Timelines

| Type of Deviation | Report to Sponsor | Method |
|--|--|---|
| Subject safety, rights or welfare; OR Data integrity; OR Compromise the statistical analysis of the study; OR Lack of Informed Consent; OR Inclusion/Exclusion | Within 24 hours of study staff becoming aware of event | Initial: Phone/Email to Sponsor Complete CRF |
| All other protocol deviations | Per protocol visits | Complete CRF |

13.0 PREMATURE STUDY TERMINATION

Both the Sponsor and the Principal Investigator (PI) reserve the right to terminate the clinical investigation at any time. Should this be necessary, the procedures will be arranged on an individual basis after review and consultation by both parties. In terminating the clinical

investigation, the 3M study team and the Principal Investigator will assure that adequate consideration is given to the protection of the subject's interests.

This study may be temporarily suspended or prematurely terminated if there is sufficient reasonable cause. Written notification, documenting the reason for study suspension or termination, will be provided by the suspending or terminating party to study participants, participating Investigators, IRB/EC's and regulatory authorities. If the study is prematurely terminated or suspended, the Principal Investigator (PI) will promptly inform study participants, the IRB/EC's, and Sponsor and will provide the reason(s) for the termination or suspension. Study participants will be contacted, as applicable, and be informed of changes to study visit schedule.

Circumstances that may warrant termination or suspension include, but are not limited to:

- Determination of unexpected, significant, or unacceptable risk to participants
- Demonstration of efficacy that would warrant stopping
- Insufficient compliance to Clinical Investigation Plan requirements
- Data that are not sufficiently complete and/or evaluable
- Determination that the primary endpoint has been met
- Determination of futility

Suspended studies may resume once concerns about safety, Clinical Investigation Plan compliance, and data quality are addressed, and satisfy the Sponsor, IRB/EC and regulatory authorities.

14.0 MONITORING

Study monitoring is conducted to ensure that the rights, safety and well-being of study participants are protected, that the reported study data are accurate, complete, and verifiable, and that the conduct of the study is in compliance with the currently approved Clinical Investigation Plan (CIP), with GCP, and with applicable regulatory requirement(s).

3M or its designee, as Sponsor of this clinical investigation, is responsible for ensuring the proper conduct of the clinical investigation with regard to CIP adherence and validity of the data recorded on the CRFs. 3M, has therefore assigned study monitor(s) to this clinical investigation. The progress of the clinical investigation will be monitored by:

- Periodic and/or remote review
- Telephone communications
- Review of CRFs and source documents (e.g. subject records)

The study monitor(s), other authorized representatives of the Sponsor, representatives of the IRB/EC, or regulatory authorities may inspect all documents and records required to be maintained by the Investigator, including but not limited to, subject records (office, clinic, or hospital) for the participants in this study. The clinical study site will permit access to such records. The Investigator will give 3M study monitor(s) direct access to source documents that support data on the CRFs. This includes any electronic records.

Investigator non-compliance of required study responsibilities will require Sponsor sanctions to alleviate the non-compliance. Including corrective and preventative actions up to and including disqualification.

Details of clinical site monitoring are documented in a Monitoring Plan (MP). The MP describes in detail who will conduct the monitoring, at what frequency monitoring will be done, at what level of detail monitoring will be performed, and the distribution of monitoring reports.

Independent audits may be conducted by GCP ClinPlus Co., Ltd, CHINA to ensure monitoring practices are performed consistently across all participating sites and that monitors are following the MP.

15.0 ROLE OF SPONSOR REPRESENTATIVE

In addition to study monitoring, the Sponsor, or their representatives may conduct the following tasks during this study:

- Audits of the Investigator
- Provision of technical support/product specific training for the study device

16.0 DEVICE ACCOUNTABILITY

The device(s) under investigation will not be distributed to the investigational site until all agreements between the site and 3M are finalized and IRB/EC approval has been obtained.

3M requires that Investigators maintain device accountability and security of the devices at all times. The Investigator or designee will:

- Maintain and account for devices at the Investigator site
- Keep devices in a secure storage area, accessible only to authorized individuals.
- Dispense devices only to subjects properly enrolled in and eligible for the study.
- Return all unused investigational materials to the Sponsor at the end of the study or dispose of as agreed upon.

16.1 Device Labeling

Devices utilized in this study will be labelled according to applicable regulations. A sample label will be retained in the Investigator Site File.

16.2 Additional Study-Specific Equipment/Device(s)

Additional study-specific equipment/devices used in this study shall be maintained, calibrated (if applicable) and ensured to be functioning correctly during the study, in accordance with this study Clinical Investigation Plan or applicable site policy and regulatory requirements.

The Sponsor should be notified of any anticipated or known issues with the device functionality that may impact the study conduct or outcome.

17.0 CONFIDENTIALITY

Participant confidentiality and privacy is strictly held in trust by the participating Investigators, their staff, and the Sponsor(s) and their authorized representatives. This confidentiality is extended to cover testing of biological samples and genetic tests in addition to the clinical information relating to participants. Therefore, the Clinical Investigation Plan, documentation, data, and all other information generated will be held in strict confidence. No information concerning the study, or the data will be released to any unauthorized third party without prior written approval of the Sponsor. All research activities will be conducted in as private a setting as possible.

Study data, which is for purposes of statistical analysis and scientific reporting, will be transmitted to and stored at 3M or approved supplier. This will not include the participant's contact or identifying information. Rather, individual participants and their research data will be identified by a unique study identification number. The electronic data capture system used by clinical sites and by 3M research staff will be secured and password protected. At the end of the study, all study databases will be de-identified and archived at 3M or approved supplier.

17.1 Future Use of Stored Collected Specimens

With the participant's approval and as approved by the local IRB/EC, de-identified biological samples will be stored at 3M with the same goal as the sharing of data with the 3M researchers.

During the conduct of the study, an individual participant can choose to withdraw consent to have biological specimens stored for future research. However, withdrawal of consent with regard to biosample storage may not be possible after the study is completed.

18.0 DATA HANDLING AND RECORD KEEPING

Data collected for this study will be analyzed and stored at 3M or an approved supplier for use by researchers including those outside of the study. Permission to transmit, store and use data outside of the study will be included in the informed consent.

18.1 Data Collection and Management Responsibilities

Data collection is the responsibility of the clinical study staff at the site under the supervision of the site Investigator. The Investigator is responsible for ensuring the accuracy, completeness, legibility, and timeliness of the data reported.

All source documents should be completed in a neat, legible, permanent and un-editable manner to ensure accurate interpretation of data. Data recorded in the electronic case report form (eCRF) derived from source documents must be consistent with the data recorded on the source documents.

Data (including adverse events (AEs), concomitant medications, and expected adverse event data) will be entered into a 21 CFR Part 11-compliant data capture system provided by 3M. The data system includes password protection and internal quality checks, such as automatic range checks, to identify data that appear inconsistent, incomplete, or inaccurate.

18.2 Study Records Retention

The study participant's information will be securely stored at each clinical site for internal use during the study. At the end of the study, all records will continue to be kept in a secure location for as long a period as dictated by the reviewing IRB/EC, Institutional policies, regulatory authorities or Sponsor requirements.

No records will be destroyed without the written consent of the Sponsor. It is the responsibility of the Sponsor to inform the Investigator when these documents no longer need to be retained.

18.3 Sponsor Oversight

Routine review of submitted study information by the Sponsor will be conducted to ensure Clinical Investigation Plan compliance. Items reviewed include but are not limited to: adverse events, deviations, number of withdrawn/terminated subjects; which all may impact the completion of the study. Appropriate measures may be taken to ensure Investigator compliance with the Clinical Investigation Plan.

19.0 STATISTICAL CONSIDERATIONS

This is a prospective, randomized, open-label, parallel-group controlled, single-center study designed to explore whether the subject product effectively reduces bacterial colonization in comparison with the control product. Subjects will be divided into two groups based on the random number table.

For continuous data, descriptive statistics will include the number of subjects, mean, standard deviation, median, minimum and maximum values. For categorical data, descriptive summaries will be made by frequency and percentage. Unless otherwise specified, a two-sided test will be used for all statistical tests, and a p-value of less than 0.05 will be considered statistically significant for the difference being tested.

19.1 Statistical Hypotheses

19.2 Sample Size Determination

This study will use a positive two-sided Z test for continuity calibration and use the O'Brien-Fleming expenditure function to determine the test boundary. Assuming a baseline value of 18.7% for CVC tips colonization rate in the control group (this figure is reported by a domestic epidemiological survey) and a reduction rate of 50.0%, each group should contain at least 220 patients with CVC to reach 80% likelihood at 5% significance level. A total of 440 valid cases are required in both groups combined. An interim analysis is scheduled for this study and will be conducted after completion of follow-up visits of 220 subjects to correct for the pre-defined sample size.

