9.0 POINT OF ENROLLMENT AND EXIT

9.1 Point of Enrollment

Following recruitment and eligibility screening, a subject will sign the informed consent form. A subject is considered enrolled in this study at time the Informed Consent process has been completed.

Eligible and consented subjects will be assigned a unique subject identification number, which will not contain information that could identify the subject.

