3.2 Study Population and Sample Size

440 subjects who meet the inclusion/exclusion criteria will be enrolled. Subjects will be adult voluntary clinical subjects, of either sex, at least 18 years of age, who are ICU patients undergoing deep venous catheterization (DVC), in which a CVC catheter must be used while other types of catheters such as hemodialysis, PICCO, and floating catheters may be used concurrently.

This study will use a positive two-sided Z test for continuity calibration and use the O'Brien-Fleming expenditure function to determine the test boundary. Assuming a baseline value of 18.7% for CVC tips colonization rate in the control group (this figure is reported by a domestic epidemiological survey) and a reduction rate of 50.0%, each group should contain at least 220 patients with CVC to reach an 80% likelihood at 5% significance level. A total of 440 valid cases are required in both groups combined. An interim analysis is scheduled for this study and will be conducted after completion of follow-up visits of 220 subjects to correct for the pre-defined sample size.

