6.3 Efficacy Evaluation

6.3.1 Primary Efficacy Evaluation

(1) Evaluation Indicators

Occurrence rate of bacterial colonization of the CVC tip segment and skin at the insertion site after extubation (number of culture-positive cases/total catheters × 100%)

Primary endpoint: Positive rates of catheter tip cultures and sampling cultures of skin surrouding the insertion site in patients with deep vein indwelling catheterization after CVC tubes were removed.

(2) Evaluation method

FAS and PPS were used for both total catheter count and participant level evaluation. If more than one catheter of the same type was available for the same participant and the culture results were inconsistent, a positive culture result was taken for that participant when participant-level analysis was performed.

Describe the number and percentage of cases of bacterial colonization of the CVC tip segment and skin at the insertion site after extubation in both groups, and compare the two groups using a chi-square test or Fisher's exact test.

In addition, because some subject may have two or more than two CVC, which are interrelated, a generalized mixed linear model was developed to evaluate the difference in the occurrence rate of bacterial colonization between the two groups, using the occurrence rate of bacterial colonization of the CVC tip segment after extubation and the occurrence rate of bacterial colonization of the skin at the CVC insertion site after extubation as dependent variables, group as a fixed effect, and insertion site, skin infection of baseline insertion site, and their interaction as random effects, respectively.

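### The stated 80% power at 220 per arm fits an uncorrected test, not the continuity-corrected Z test that the sizing paragraph appears to name

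*Protocol*

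**What the plan says.** Protocol 19.2 names the sizing test: "This study will use a positive two-sided Z test for continuity calibration", with an O'Brien-Fleming spending function for the boundaries. The inputs follow: "Assuming a baseline value of 18.7% for CVC tips colonization rate in the control group", and a 50% reduction. The conclusion is that "each group should contain at least 220 patients with CVC to reach 80% likelihood at 5% significance level", and then: "A total of 440 valid cases are required in both groups combined". SAP 3.2 repeats this almost word for word: "each group should contain at least 220 patients with CVC to reach an 80% likelihood at 5% significance level".

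The analysis sections name different tests. Protocol 19.4 gives chi-square or Fisher's exact test for CVC tip colonization. SAP 6.3.1 says to "compare the two groups using a chi-square test or" Fisher's exact test. Neither mentions a continuity correction or says how to choose between the two. SAP 6.1 sets the final two-sided level at 0.048, and SAP 8 sets the interim level at 0.005.

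On numbers, the Protocol synopsis, Protocol 6.0 and SAP 3.2 enrol 440. Protocol 9.1 fixes the moment: "A subject is considered enrolled in this study at time the Informed Consent process has been completed". Protocol 9.2 treats a patient who leaves the ICU with the CVC still in place as lost to follow-up.

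**The concern.** The sizing paragraph joins a test, a pair of rates, a significance level, a sample size and a power. If the test is continuity-corrected, these five do not fit together, and the only power figure in the plan belongs to a different test from the one beside it.

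The choice also matters later. Protocol 19.5 and SAP 8 recalculate the sample size at the interim, and neither says which test or formula to use. Corrected and uncorrected versions differ by about 20 per arm, so the interim team could reach different totals from the same data.

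**Working it through.** **Inputs.** Control rate p1 = 0.187 and 50% reduction, so p2 = 0.0935 (Protocol 19.2, SAP 3.2). Difference d = 0.0935; mean rate 0.14025. Allocation 1:1 (Protocol 10.2.1). Two-sided 0.05 (Protocol 19.0) or 0.048 at the final look (SAP 6.1). Power 80%, z = 0.8416.

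**Step 1: reproduce 220 without correction.** The pooled-variance formula is

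n = [z_a·√(2·p̄·(1−p̄)) + z_b·√(p1(1−p1) + p2(1−p2))]² / d²

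with √(2 × 0.14025 × 0.85975) = 0.4911, √(0.23679) = 0.4866 and d² = 0.008742.

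- At 0.05: (1.9600 × 0.4911 + 0.8416 × 0.4866)² / 0.008742 = 215.3, so 216 per arm.
- At 0.048: z_a = 1.9774 gives 218.0, so 219 per arm.

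The stated 220 is reproduced.

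**Step 2: add the continuity correction.** The usual adjustment is n_c = (n/4)·[1 + √(1 + 4/(n·d))]².

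- At 0.05: n = 215.3 gives 236.2, so 237 per arm.
- At 0.048: n = 218.0 gives 238.9, so 239 per arm.

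**Step 3: power at 220 per arm.** By formula, power = Φ[(d − c − z_a·se0)/se1], with se0 = 0.4911/√220 = 0.03311, se1 = 0.4866/√220 = 0.03281, and c = 0 or 1/220. Exact power sums binomial probabilities over all outcomes that the pooled test rejects.

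| Test at 220 per arm | Level | Formula | Exact |
|---|---|---|---|
| Uncorrected | 0.05 | 80.8% | 81.6% |
| Uncorrected | 0.048 | 80.4% | 80.9% |
| Corrected | 0.05 | 76.8% | 77.2% |
| Corrected | 0.048 | 76.3% | 77.2% |
| Fisher's exact | 0.05 | – | 77.9% |
| Fisher's exact | 0.048 | – | 77.2% |

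By exact enumeration the corrected test first reaches 80% at 233 per arm (0.05) or 235 (0.048).

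**Step 4: can another reading rescue 220 with the correction?** The two-look O'Brien-Fleming design needs 217 to 218 per arm uncorrected and 238 to 239 corrected, so the interim look explains only 1 to 3 patients per arm. One-sided versions give 170 to 173 uncorrected and 191 to 194 corrected. Neither matches.

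**Step 5 (secondary): losses.** The documents give no loss rate, so 5%, 10% and 15%, equal in both arms, are assumptions. Starting from 220 randomised per arm, with an uncorrected chi-square at 0.048 and exact power:

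| Assumed loss | Evaluable per arm | Power, losses excluded | Rates if filled as positive | Power, filled as positive |
|---|---|---|---|---|
| 5% | 209 | 79.1% | 22.8% v 13.9% | 67.4% |
| 10% | 198 | 77.0% | 26.8% v 18.4% | 55.6% |
| 15% | 187 | 74.3% | 30.9% v 22.9% | 46.3% |

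The filled rate is p(1 − L) + L for loss L, which shrinks the difference to d(1 − L) and raises the variance.

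**The case against.** - **The test is inferred.** The phrase in both documents reads like a rough translation and never says correction. That stands. Continuity correction is the natural meaning for a Z test on two proportions, but it remains an inference. Its size is not given either: half the conventional amount, 1/(2n), would leave power at 220 just under 80% at 0.05.
- **The analysis is a chi-square test, for which 220 is enough.** This largely stands. With 220 × 0.187 ≈ 41 and 220 × 0.0935 ≈ 21 expected positives, ordinary practice would use chi-square, and uncorrected it has about 81% power. A reader might infer that the trial is underpowered and must recruit 17 to 19 more per arm. The documents do not support that: the fault is a mismatch between the named sizing test and the stated figure. It is still a fault, because neither analysis section excludes a correction, and Fisher's test, also permitted, falls short of 80%.
- **The gap is small.** True: about 3 to 4 points of power.
- **Losses are dealt with at the interim.** A reader might infer that the plan makes no provision for losses. That is too strong: SAP 8 takes account of dropout when it recalculates the sample size, and the total can rise but not fall below the protocol figure. What is absent is an allowance at the start.
- **The low power figures under filling are a separate matter.** Agreed. They come from the worst-case rule in SAP 7.3 and from assumed loss rates, not from the continuity correction. SAP 7.3 also reports the unfilled result, and Protocol 19.6 says efficacy data will not be imputed, which conflicts with Protocol 19.3.

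**Conclusion.** The point holds as an inconsistency in the sizing statement. If the named Z test is continuity-corrected with the conventional 1/n, 80% power needs 237 to 239 per arm by formula (233 to 235 exactly), and 220 gives about 76 to 77%. The stated 220 with 80% is right for an uncorrected test. The conclusion rests on the plan's own rates and on reading the phrase as continuity correction; it does not show that the sample size is inadequate for the analysis most likely to be run.

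The secondary point is that 440 enrolled, counted at consent, equals the 440 valid cases required, so any loss before the interim recalculation comes out of the stated power. For assumed losses of 5 to 15%, power runs from about 79% down to 74% if losses are excluded, and from about 67% down to 46% if they are filled as positive.

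**What to change.** In Protocol 19.2 and SAP 3.2, name one test and use it for sizing, for the primary analysis (Protocol 19.4, SAP 6.3.1) and for the interim recalculation (Protocol 19.5, SAP 8). Either:

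1. name the uncorrected chi-square test, remove the continuity wording, and state about 81% power for 220 evaluable per arm at 0.048; or
2. keep the continuity-corrected test and restate the power as about 77% at 220 per arm.

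The first agrees better with the analysis sections. If Fisher's test stays as an alternative, give the rule that triggers it.

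Say whether 440 counts consented, randomised or evaluable patients, and add a short table of power over a range of assumed losses under the missing-data rule that will apply, as in step 5.

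The cost is wording in the sizing, analysis and interim sections. No extra enrolment is needed. Under the second option the stated power becomes a little less favourable.
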